#### 2.4.4.1.2 Sensitivity analysis of primary efficacy endpoint

The following sensitivity analyses will be performed for the primary endpoint.

An analysis of covariance (ANCOVA) with the missing data imputed by LOCF will be performed on the primary efficacy variable. The model will include treatment (Renvela or placebo) and screen serum phosphorus class ( $\geq 5.5$  -  $6.0$  mg/dL [ $1.78$  -  $1.94$  mmol/L] or  $>6.0$  mg/dL [ $1.94$  mmol/L]) and baseline serum phosphorus level as covariates. The adjusted mean difference of primary endpoint between two treatment groups will be provided as well as the 95% confidence interval and P-value.

The Markov Chain Monte Carlo (MCMC) method for multiple imputation will be used to account for missing values in change from baseline in serum phosphorus at Week 8. The imputation model will include baseline serum phosphorus level and all serum phosphorus level at all post-baseline visits stratified by treatment group and screen serum phosphorus class. The seed used for these imputations will be 14011. A minimum value of 0 will be specified in order to avoid negative imputed Phosphorus level.

Missing value in serum phosphorus will be imputed 100 times to generate 100 data sets with complete serum phosphorus values at Week 8. The change from baseline will be derived from observed and imputed serum phosphorus values. The completed data sets will be analyzed using an ANCOVA model with treatment groups, screen serum phosphorus class and baseline serum phosphorus level as covariates. The results from the 100 analyses will be combined using SAS PROC MIANALYZE.

#### 2.4.4.1.3 Subgroup analysis

Subgroup analysis of primary endpoint will be conducted for exploratory purpose. The subgroup analysis include:

- Screening serum phosphorus level ( $\geq 5.5 - 6.0 \text{ mg/dL}$  [ $1.78 - 1.94 \text{ mmol/L}$ ] or  $> 6.0 \text{ mg/dL}$  [ $1.94 \text{ mmol/L}$ ])
- Age (quartiles)
- Baseline eGFR (quartiles)
- Main cause of CKD (diabetes, hypertension and glomerulonephritis)
- Average daily dose (quartiles)
- Average daily dose (quartiles) \* Screening serum phosphorus level ( $\geq 5.5 - 6.0 \text{ mg/dL}$  [ $1.78 - 1.94 \text{ mmol/L}$ ] or  $> 6.0 \text{ mg/dL}$  [ $1.94 \text{ mmol/L}$ ])
- Screening serum phosphorus level ( $\leq 7.5 \text{ mg/dL}$  [ $2.42 \text{ mmol/L}$ ] or  $> 7.5 \text{ mg/dL}$  [ $> 2.42 \text{ mmol/L}$ ])

#### **2.4.4.2 Analyses of secondary efficacy endpoints**

All secondary endpoints will be analyzed using the mITT population.

Descriptive statistics (number, mean, SD, median, Q1, Q3, minimum, and maximum) will be provided by treatment for all continuous secondary variables at the scheduled visits.

All continuous secondary efficacy variables, ie, the change from baseline in serum lipids (total cholesterol and LDL-C), calcium-phosphorus product at Week 8, iPTH at Week 8 and serum phosphorus at Week 4 will be analyzed using the same test described in [Section 2.4.4.1.1](#). For total cholesterol and LDL-C, sensitivity analysis of multiple imputation will not be applied. The same procedure for handling missing assessments/early discontinuation will also be applied as for the primary variable.

Proportion of patients reaching the target serum phosphorus level at Week 8 will be compared by treatment assignment (Renvela or placebo) using a Cochran-Mantel-Haensel method stratified by randomization strata (screening serum phosphorus:  $\geq 5.5 - 6.0 \text{ mg/dL}$  [ $1.78 - 1.94 \text{ mmol/L}$ ] or  $> 6.0 \text{ mg/dL}$  [ $1.94 \text{ mmol/L}$ ]), the proportion difference between Renvela and placebo group and 95% confidence intervals will be calculated.

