10.3.4 Handling of patients after permanent treatment discontinuation

Patients will be followed-up according to the study procedures as specified in this protocol up to the scheduled date of study completion, or up to recovery or stabilization of any AE to be followed-up as specified in this protocol, whichever comes last.

If possible, and after the permanent discontinuation of treatment, the patients will be assessed using the procedure normally planned for the last dosing day with the IMP.

If applicable, instruct patient to resume their previous phosphate binder(s).

All cases of permanent treatment discontinuation should be recorded by the Investigator in the appropriate pages of the e-CRF when considered as confirmed. The investigator will retrieve any unused treatment and instruct the patient to resume their phosphate binder(s), if applicable.

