## 2.4.4 Analyses of efficacy endpoints

### 2.4.4.1 Analysis of primary efficacy endpoint

#### 2.4.4.1.1 Primary efficacy analysis

The change from baseline in serum phosphorus at Week 8 as defined in [Section 2.1.3.1](#) will be compared between the Renvela group to the placebo group in the mITT population using stratified Wilcoxon rank sum tests considering randomization strata (screening serum phosphorus [ $\geq 5.5$  -  $6.0$  mg/dL or  $>6.0$  mg/dL]). The statistical test will be two-sided tests at a nominal 5% significance level.

If a patient discontinues the treatment prematurely or does not have serum phosphorus value at Week 8, the last post-baseline on-treatment serum phosphorus measurement during the 8-week double-blind period will be used for the calculation of Week 8 (Last Observation Carried Forward [LOCF] procedure).

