#### **2.4.4.3 Multiplicity issues**

In order to handle multiple key endpoints, the overall type-I error will be controlled by the use of a fixed sequence approach. Statistical significance of the primary parameter at the 0.05 alpha level is required before drawing inferential conclusions about first secondary endpoint. Inferential conclusions about successive secondary endpoints require statistical significance of the prior one. The statistical inference order is as follows:

- The change from baseline in serum phosphorus at Week 8
- The change from baseline in total cholesterol at Week 8
- The change from baseline in LDL-C at Week 8
- The change from baseline in calcium-phosphorus product at Week 8
- The change from baseline in iPTH level at Week 8

- Percentage of patients reaching the target serum phosphorus level (4.6 mg/dL [1.49 mmol/L], inclusive) at Week 8
- The change from baseline in serum phosphorus level at Week 4

This fixed hierarchical approach will ensure a strong control of the overall type-I error rate at the 0.05 level. No further adjustments will be made for other secondary endpoints, for which p-values will be provided for descriptive purpose only (no claim).

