#### **2.5.2 Missing data**

For categorical variables, patients with missing data are not included in calculations of percentages unless otherwise specified. When relevant, the number of patients with missing data is presented.

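### Does Week 8 target attainment lack a missing-data rule that its place in the testing sequence requires?

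*SAP*

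**What the plan says.** For the primary endpoint, SAP 2.4.4.1.1 provides that if a patient stops treatment early or has no Week 8 phosphorus, "the last post-baseline on-treatment serum phosphorus measurement during the 8-week double-blind period will be used for the calculation of Week 8". SAP 2.4.4.2 carries this to the secondary endpoints: "The same procedure for handling missing assessments/early discontinuation will also be applied as for the primary variable". That sentence ends a paragraph about the continuous variables. The CMH comparison of target attainment comes next, in its own paragraph, without a missing-data rule. Protocol 11.4.2.2 has the same layout.

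Four other places bear on the point:

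- SAP 2.5.1, on data handling for secondary efficacy variables of any type, only refers to SAP 2.4.4.2.
- SAP 2.5.2 gives a general default: "For categorical variables, patients with missing data are not included in calculations of percentages unless otherwise specified".
- SAP 2.5.3 sets analysis windows for all analyses. For Week 8 (Day 51 to 64) it prefers the measurement closest to the last dose.
- SAP Appendix B lists multiple imputation as supportive for target attainment. SAP 2.4.4.1.2 describes that method only for change from baseline: "The completed data sets will be analyzed using an ANCOVA model with treatment groups" and two further covariates.

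SAP 2.4.4.3 places target attainment sixth, counting the primary endpoint, and states that "Inferential conclusions about successive secondary endpoints require statistical significance of the prior one". The protocol reports an odds ratio for this endpoint and the SAP a difference in proportions. SAP 1.5 does not list that change.

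**The concern.** Read literally, the LOCF sentence covers only continuous variables, nothing in the CMH paragraph displaces the SAP 2.5.2 default, and patients without a Week 8 value would leave the denominator. Two analysts could then report different numbers analysed and different percentages for an endpoint tested at the 0.05 level, with Week 4 phosphorus waiting behind it.

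The readings can also classify the same patient differently. Protocol 10.3.4 keeps patients who stop treatment in the study: "Patients will be followed-up according to the study procedures as specified in this protocol up to the scheduled date of study completion". It also has them go back to an earlier binder where they had one. A Week 8 sample may therefore exist but have been taken off study treatment. LOCF would use the last on-treatment value. A reading without LOCF might use the later one.

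If the choice were truly open and made after unblinding, it could decide a result near the 5% boundary.

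**Working it through.** **1. The plan's own figure.** SAP 1.3 assumes a difference of 1 mg/dL, SD 2, two-sided 5% and 90% power. A two-sample t-test with standardised effect 1/2 = 0.5 needs 85.03 per arm, rounded up to 86 (power 90.3%). With 15% dropout, 86/0.85 = 101.2, against the stated 101 per arm. The figure reproduces and does not depend on this point. The documents give no power for target attainment.

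**2. Which rule the text yields.** The endpoint asks whether Week 8 phosphorus is at or below 4.6 mg/dL. SAP 2.4.4.1.1 defines what stands in for Week 8 phosphorus when a patient stops or the sample is missing. Once that value is derived, target status is known for every mITT patient with an on-treatment post-baseline measurement. The SAP 2.5.2 default acts only on patients whose data are missing and gives way where another rule is specified. SAP 2.5.1 sends all secondary efficacy variables to SAP 2.4.4.2, and the only procedure found there is that of the primary variable. LOCF is the natural derivation. What remains is the few patients whose only post-baseline phosphorus was taken off treatment.

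**3. Samples taken after stopping.** The SAP 2.5.2 default is about denominators. It does not say that an off-treatment value replaces an on-treatment one. SAP 2.5.3 favours the value nearest the last dose within the Week 8 window. It does not settle an early stopper whose only in-window sample is off treatment, but the LOCF sentence does, because it applies to early stopping as well as to a missing value.

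**4. Size, if the default were used after all.** Inputs: 101 per arm, SD 2 and effect 1 mg/dL (SAP 1.3); placebo change -0.19 from the dialysis trial in protocol section 4. Assumptions: normal changes, baseline 6.5 mg/dL, and stoppers with no Week 8 sample but a usable earlier one. At 15% stopping, 0.15 × 101 ≈ 15 patients per arm are affected.

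Being at target means a change of at most 4.6 - 6.5 = -1.9.

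- Renvela: Φ((-1.9 + 1.19)/2) = 0.361
- Placebo: Φ((-1.9 + 0.19)/2) = 0.196

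Exclusion keeps these rates with n = 101(1 - d) per arm, where d is the stopping rate. LOCF uses n = 101 and rate p(1 - d) + k·p·d, where k is how often stoppers are at target relative to the others. Power = Φ((|p1 - p2| - 1.96·s0)/s1), with s0 the pooled and s1 the unpooled standard error. This unstratified test stands in for the CMH test.

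At 15%/15%:

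- Exclusion (n = 85.85): s0 = 0.0684, s1 = 0.0673; (0.1650 - 0.1341)/0.0673 = 0.459, power 67.7%.
- LOCF, k = 0.5 (0.334 vs 0.182): s0 = 0.0616, s1 = 0.0606; (0.1526 - 0.1207)/0.0606 = 0.527, power 70.1%.

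| Stopping, Renvela/placebo | Exclusion | LOCF, k = 0.5 |
|---|---|---|
| 5%/5% | 72.6% | 73.2% |
| 15%/15% | 67.7% | 70.1% |
| 20%/10% | 67.8% | 61.9% |
| 10%/20% | 67.2% | 77.4% |

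With k = 1, LOCF gives about 75%. At 15%/15% and k = 0.5, a baseline of 5.5 gives 73.7% (exclusion) and 74.6% (LOCF), and a baseline of 7.5 gives 53.1% and 56.1%.

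**5. Larger effects.** With the dialysis trial's Renvela change of -2.14, the Renvela rate is Φ((-1.9 + 2.14)/2) = 0.548 and power exceeds 99% under both rules at 15%/15% and at 20%/10%. The open-label not-on-dialysis study in protocol section 4 had 70% to 75% at target (range 2.7 to 4.6 mg/dL). Taking 70% against 19.6%, power rounds to 100% under both rules. Against an assumed placebo rate of 40% it is 98% under both at 15%/15%, and against 50% it is about 77% and 76%.

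**The case for a change.** The strongest case is that a confirmatory endpoint should not rest on inference. The literal wording permits exclusion, and the choice can cross the boundary. With assumed completer rates of 40% and 25% and 20 Renvela and 10 placebo patients missing, exclusion gives 32/81 vs 23/91, p = 0.046. LOCF with stoppers at target half as often gives 36/101 vs 24/101, p = 0.065. Even with 15 missing in each arm, p moves from 0.051 (34/86 vs 22/86) to 0.046 (37/101 vs 24/101).

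It stands that the sentence is in the wrong paragraph for a strict reader, and that a borderline result could tip. But these examples are built close to 0.05, and they matter only if the alternative is a live choice. The structure of the endpoint and the routing in SAP 2.5.1 both lead to LOCF.

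Two further points are correct as observations. Appendix B names multiple imputation without saying how imputed target status is analysed and pooled, but that analysis is supportive and does not decide the test. The change from odds ratio to proportion difference alters the reported estimate and leaves the CMH p-value as it was.

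One could also ask for an analysis that counts early stoppers as not at target. In the 15%/15% illustration it gives 30.7% vs 16.7%, or 14.0 points. That is a different way of treating discontinuation. The plan contains no error that it would repair.

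**Conclusion.** The wording is loose and the intended analysis is recoverable. Target status follows from the Week 8 phosphorus of the primary analysis, with LOCF, in the mITT population. A sentence saying so would record what analysts would do anyway. The primary analysis and the sample size are untouched.

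If exclusion were used instead, the illustrated power would differ by 2.4 percentage points at 15%/15% stopping and by 0.6 at 5%/5%. Gaps of 6 to 10 points appear only when stopping differs between arms and the true effect is as modest as planned. With effects of the size in the cited sevelamer studies the rule hardly matters at equal stopping, unless the placebo rate at target is itself near 50%. These figures rest on an assumed baseline, normal changes, assumed stopping rates and k = 0.5, since the documents give no placebo attainment rate. They also cover only stoppers without a Week 8 sample. The effect of off-treatment Week 8 samples was not quantified.

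The effect-measure mismatch and the unstated pooling rule are clerical and supportive matters that do not alter any tested result.

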#### **2.4.4.3 Multiplicity issues**

In order to handle multiple key endpoints, the overall type-I error will be controlled by the use of a fixed sequence approach. Statistical significance of the primary parameter at the 0.05 alpha level is required before drawing inferential conclusions about first secondary endpoint. Inferential conclusions about successive secondary endpoints require statistical significance of the prior one. The statistical inference order is as follows:

- The change from baseline in serum phosphorus at Week 8
- The change from baseline in total cholesterol at Week 8
- The change from baseline in LDL-C at Week 8
- The change from baseline in calcium-phosphorus product at Week 8
- The change from baseline in iPTH level at Week 8

- Percentage of patients reaching the target serum phosphorus level (4.6 mg/dL [1.49 mmol/L], inclusive) at Week 8
- The change from baseline in serum phosphorus level at Week 4

This fixed hierarchical approach will ensure a strong control of the overall type-I error rate at the 0.05 level. No further adjustments will be made for other secondary endpoints, for which p-values will be provided for descriptive purpose only (no claim).

#### **2.4.5 Analyses of safety data**

The summary of safety results will be presented by treatment group. No formal inferential testing will be performed. Summaries will be descriptive in nature.

##### ***General common rules***

All safety analyses will be performed on the safety population as defined in [Section 2.3.2](#), unless otherwise specified, using the following common rules:

- Safety data in patients who do not belong to the safety population (eg, exposed but not randomized) will be listed separately.
- The baseline value is defined as last available value obtained up to the date and time of the first double-blind IMP administration, except other specified.
- The potentially clinically significant abnormality (PCSA) values are defined as abnormal values considered medically important by the Sponsor according to predefined criteria/thresholds based on literature review and defined by the Sponsor for clinical laboratory tests, vital signs, and ECG (see 0). In case the threshold defined in the PCSA list for a given lab parameter is below the ULN, the following PCSA criterion will be used for the PCSA analysis:  $>\text{PCSA threshold}$  or  $>\text{ULN}$  (if  $\text{ULN} \geq \text{PCSA threshold}$ ).
- PCSA criteria will determine which patients had at least 1 PCSA during the treatment-emergent adverse event period, taking into account all evaluations performed during the treatment-emergent adverse event period, including nonscheduled or repeated evaluations. The number of all such patients will be the numerator for the on-treatment PCSA percentage.
- The treatment-emergent PCSA denominator by group for a given parameter will be based on the number of patients assessed for that given parameter in the treatment-emergent adverse event period by treatment group on the safety population.

All measurements, scheduled or unscheduled, will be assigned to analysis windows defined in [Section 2.5.3](#), Table 2 in order to provide an assessment for Week 2 to Week 8 time points.

- For quantitative safety parameters based on central laboratory/reading measurements, descriptive statistics will be used to summarize results and change from baseline values by visit and treatment group. Summaries will also be provided for the last on-treatment value. The last on-treatment value is defined as the value collected at the same day/time of the last administration of IMP. If this value is missing, this endpoint value will be the closest value prior to the last dose intake.

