11.4.3 Analyses of safety data

The summary of safety results will be presented by treatment group. No formal inferential testing will be performed. Summaries will be descriptive in nature.

All safety analyses will be performed on the Safety population using the following common rules:

- The baseline value is defined generally as the last available value before first dose administration.

The following definitions will be applied to laboratory parameters and vital signs.

- The potentially clinically significant abnormality (PCSA) values are defined as abnormal values considered medically important by the Sponsor according to predefined criteria/thresholds based on literature review and defined by the Sponsor for clinical laboratory tests and vital signs.
- PCSA criteria will determine which patients had at least 1 PCSA during the on-treatment period, taking into account all evaluations performed during the on-treatment period, including unscheduled or repeated evaluations. The number of all such patients will be the numerator for the on-treatment PCSA percentage.

The observation period will be divided into three segments: pre-treatment, on-treatment and post-treatment

- The pre-treatment period is defined as the time between the date of the informed consent and the start of study medication.
- The on-treatment period is defined as the time from the first dose of study medication up to 3 days after the last dose of study medication administration.
- The post-treatment period is defined as the time starting 4 days after last dose of study medication administration (after the on-treatment period) to the end of the study.

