#### ***Observation period***

The observation of safety data will be as follows:

- Pre-treatment period: The pre-treatment observation period is defined from the signed informed consent up to the first dose of double-blind IMP.
- Treatment Emergent Adverse Event (TEAE) period: The TEAE observation period is defined as the time from the first dose of double-blind IMP to the last dose of double-blind IMP+3 days.
- Post-treatment period: The post-treatment observation period is defined as the time starting the day after the end of the TEAE period up to the end of the study (see definition in Protocol Section 6.2.1).

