#### **2.4.5.3 Analyses of laboratory variables**

The summary statistics (including number, mean, median, standard deviation, minimum and maximum) of all laboratory variables (central laboratory values and changes from baseline) will be calculated for each visit or study assessment (baseline, each post baseline time point, last on-treatment) by treatment group. This section will be organized by biological function as specified in [Section 2.1.4.3](#).

The incidence of PCSAs (list provided in 0) at any time during the treatment-emergent adverse event period will be summarized by biological function and treatment group whatever the baseline level and/or according to the following baseline status categories:

- Normal/missing
- Abnormal according to PCSA criterion

For parameters for which no PCSA criteria are defined, similar table(s) using the normal range will be provided.

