**Table 1 - Analysis windows definition**

Time point	Targeted study day	Analysis window in study days
Week 2	15	2 to 22
Week 4	29	23 to 36
Week 6	43	37 to 50
Week 8	57	51 to 64
Follow-up	71	65 ~

For the case multiple visit dates fall into the same analysis window, the one close to the targeted study day is applied. In case of two visit dates are equally close to targeted date, the original record of visit will be applied. For the Week 8, the analysis visit should use the one close to the last IMP dose intake.

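### The SAP's last on-treatment safety value drops samples taken after the last-dose day and can fall back to the pre-dose baseline

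*SAP*

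**What the plan says.** The general common rules in SAP 2.4.5 define the value in two steps. First: "The last on-treatment value is defined as the value collected at the same day/time of the last administration of IMP". If no such value exists, "this endpoint value will be the closest value prior to the last dose intake". Neither step admits a sample drawn on a later day, and the second sets no lower limit such as after first dose or post-baseline.

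The same rules count PCSAs over a wider span, "taking into account all evaluations performed during the treatment-emergent adverse event period, including nonscheduled or repeated evaluations". SAP 2.1.4 fixes that span: "The TEAE observation period is defined as the time from the first dose of double-blind IMP to the last dose of double-blind IMP+3 days". Protocol 11.4.3 gives the same span the on-treatment label: "The on-treatment period is defined as the time from the first dose of study medication up to 3 days after the last dose".

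Two other SAP rules are useful comparisons:

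- Below the windows table in SAP 2.5.3: "For the Week 8, the analysis visit should use the one close to the last IMP dose intake". This does not restrict the choice to values before the last dose.
- In the primary LOCF rule in SAP 2.4.4.1.1, "the last post-baseline on-treatment serum phosphorus measurement during the 8-week double-blind period will be used". Here the post-baseline condition is written out.

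SAP 2.4.5.3 lists the laboratory summary points as "baseline, each post baseline time point, last on-treatment".

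**The concern.** A sample 1 to 3 days after the last dose is on-treatment for the PCSA percentage but not for the last on-treatment value. That would matter little if every analyte were measured at each visit, because the fallback would then usually be a recent on-drug value. It matters here because most safety analytes are drawn only at Visit 2 (before the first dose) and again at Visit 6 or end of treatment. For those, discarding the end-of-treatment sample leaves only the pre-dose sample.

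The route is foreseeable. Protocol 10.3.4 places the end-of-treatment assessment of early stoppers after they have discontinued, and these include patients who stopped for adverse events. A completer who took the last tablet the day before Visit 6 is caught as well.

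At stake is whether the safety tables agree with one another. For one patient and one analyte, the PCSA and by-visit tables could show a post-dose result while the last-on-treatment summary shows baseline with no change, or shows nothing.

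**Working it through.** The plan states no figure on this point, so there is none to reproduce. The check is of the rule against the sampling schedule.

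**1. Analytes with no scheduled post-dose sample before Visit 6.** Inputs: the laboratory list and the exclusion of efficacy variables in SAP 2.1.4.3; the panels in protocol 1.2 (footnotes b to e), 10.1.2.1, 10.1.2.3 and 10.1.2.5.

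- Chemistry: 14 listed - 2 efficacy variables (serum phosphorus, calcium-phosphorus product) = 12. Four of these (calcium, albumin, chloride, bicarbonate) are drawn at Visits 3 to 5. 12 - 4 = 8 remain: ALT, AST, creatinine, BUN, potassium, sodium, glucose, uric acid.
- Lipids: 5 listed - 2 efficacy variables (total cholesterol, LDL-C) = 3, all drawn at Visits 2 and 6 only.
- Haematology: nothing scheduled at Visits 3 to 5.

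**2. The rule applied to the schedule.** Last-dose days 20, 35 and 57 were tried, with the end-of-treatment sample 0 to 4 days later. The comparison rule takes the last value after first dose and up to last dose + 3 days.

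| Analyte group | Sample after last dose | SAP 2.4.5 returns | Comparison rule returns |
|---|---|---|---|
| Visits 2 and 6 only | same day | that sample | that sample |
| Visits 2 and 6 only | 1 to 3 days | Day 1 (change = 0) | that sample |
| Visits 2 and 6 only | 4 days | Day 1 (change = 0) | missing |
| Visits 2 to 6 | same day | that sample | that sample |
| Visits 2 to 6 | 1 to 3 days | Day 15, 29 or 43 | that sample |
| Visits 2 to 6 | 4 days | Day 15, 29 or 43 | Day 15, 29 or 43 |

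The results in the first three rows were the same for all three last-dose days.

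**3. Two worked patients (ALT, no unscheduled test).**

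- Last tablet Day 56, Visit 6 sample Day 57. PCSA period ends 56 + 3 = Day 59, so the sample counts. It lies in the Week 8 window (Days 51 to 64), so it counts there too. Last on-treatment value: Day 1.
- Last tablet Day 30, end-of-treatment sample Day 32. PCSA period ends 30 + 3 = Day 33, so it counts. It lies in the Week 4 window (Days 23 to 36). Last on-treatment value: Day 1.

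**4. Effect on a mean.** Let f be the affected share of an arm and m the true mean change, assumed equal in affected and unaffected patients. On the literal reading:

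reported mean = (1 - f) x m + f x 0 = (1 - f) x m

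| Assumed f | Patients per arm (f x 101) | Reported / true |
|---|---|---|
| 2% | about 2 | 0.98 |
| 5% | about 5 | 0.95 |
| 10% | about 10 | 0.90 |
| 15% | about 15 | 0.85 |
| 30% | about 30 | 0.70 |

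The 15% planned dropout is not an upper limit for f: it is a planning figure, and completers can be affected. If a programmer sets the value to missing instead, n falls by the share f and the mean is not pulled towards zero.

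**The case against.** **The label.** The value is called on-treatment, protocol 11.4.3 starts that period at first dose, and SAP 2.4.5.3 lists baseline as a separate summary point. On this reading an affected patient has no last on-treatment value, and the false zero never arises. This is a fair reading, but the operative definition does not state it. Even if it is adopted, the patient's only post-dose sample, which the protocol's own period counts as on-treatment, is still lost from the summary. Zero and missing give different tables, and the SAP does not choose.

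**Different purposes.** A wide window for catching abnormalities and a stricter on-drug rule for a mean can coexist. That is true in principle, and protocol 11.4.3.2, which speaks of the last value in the treatment period without mentioning 3 days, is not contradicted. But the plan does not say that two meanings of on-treatment are intended. The Week 8 sentence in SAP 2.5.3 can also be read as only a rule for choosing between records in one window, so little weight rests on it.

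**Few patients.** The protocol synopsis makes Visit 6 the day of the last tablets, so most completers satisfy the first step. Unscheduled tests may also supply an on-drug value. Both points stand, and they are why the rule *can* return baseline rather than *will*. They do not help an early stopper who is sampled later without an extra test.

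**Unknown size.** The share f is assumed, and protocol 10.3.4 gives no interval for the end-of-treatment assessment. A sample 4 or more days after the last dose is lost under the wider window too. This also stands.

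**Conclusion.** The concern holds, as a minor one. As written, the rule excludes every sample after the last-dose day and has no post-baseline condition. For 8 of 12 safety chemistry analytes, the 3 safety lipids and all haematology it can therefore report the pre-dose value as the last on-treatment value.

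On the literal reading the mean change shrinks by the factor (1 - f), from 0.98 to 0.70 over the assumed range of 2% to 30%. This rests on equal true mean change in affected and unaffected patients. If the true mean change is near zero, the mean hardly moves. No difference between arms is claimed.

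Not affected: patients sampled on the last-dose day, PCSA counts, by-visit tables, the efficacy analyses and all hypothesis tests. Confidence in the reading of the text is high; the number of patients affected is unknown.

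**What to change.** Replace the definition in SAP 2.4.5 with: *the last post-baseline value collected after the first dose and no later than 3 days after the last dose of IMP (the TEAE period); missing if there is none.* This uses a period the plan already defines and settles what to do with a sample drawn later on the last-dose day.

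At minimum, keep the present sentence and add that the value must be post-baseline, and missing otherwise. That removes the false zero but still leaves out samples taken 1 to 3 days after the last dose. The primary LOCF text in SAP 2.4.4.1.1 should stay as it is.

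The cost is one sentence and no new data. There are three downsides:

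- Some values will be up to 3 days off drug.
- In patients withdrawn for dialysis (protocol 10.3.3; SAP 2.2) the value may come after dialysis has started. Those patients should be identifiable in the listing, although a listing flag does not take them out of the mean.
- The n will be smaller than on the literal reading, because patients with no eligible post-dose sample become missing.
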